#### 8.6.1.4. Other sensitivity analyses

Note: statistical analyses described in this section requires databases from other clinical trials. These statistical analyses may be performed on condition that these databases from other clinical trials can be recovered and pooled together. At the time of writing, it is unknown whether these analyses could be performed or not.

Further to consultation of Scientific Advice Working Party (SAWP) Committee for Medicinal Products for Human Use (CHMP) for sample size decrease, the following advice was provided: *"Although the trial is uncontrolled, it is still considered important to attempt to place the results into context by comparison with the reported efficacy of NECT in a broadly similar HAT patient population. With completion of the primary analysis of the pivotal trial for fexinidazole vs. NECT there are recent data in late stage 2 HAT that could be used to place the data obtained with acoziborole into some context. The cure rate in late stage 2 HAT in the fexinidazole pivotal study was 97.6% and DNDI is aware of the result since the trial was conducted under DNDI's auspices even though the MAH will be Sanofi. Although acoziborole will be a single dose oral treatment, the results of the acoziborole study will need to be discussed in light of the results that were obtained with NECT in late stage 2 patients. Matching on selection criteria or adjustments to account for differences between the study population and the historical/external control should be considered".*

Data presented in Table 4 concerned patients in late stage 2 (WBC in CSF > 20) and are not matched on other inclusion criteria that could affect efficacy. During the discussion meeting on November 5 in 2015 the following points were presented:

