**Figure 2. Decision Tree for the Diagnosis of HAT in the Context of the Study**

\*Preferably CATT for active screening and RDT for passive screening

\*\*Preferably in the following order: mAECT-BC (passive); mAECT (active); CTC/Woo test; Thick blood smear

CATT: Card Agglutination Test for Trypanosomiasis

Tryps: Trypanosomes

CSF: Cerebrospinal Fluid

WBC: White Blood Cell count

Pos: Positive

Neg: Negative

Screening, which consists in investigation of potential infection, will be performed by assessing clinical signs, including the presence of swollen cervical lymph nodes, and by serological tests. In the community or at hospital, serological screening will be performed using a rapid diagnostic test (RDT) or the card agglutination test for trypanosomiasis (CATT) (9).

For patients with a positive result on serological screening, tests to detect the parasite will be performed, preferably using one of the concentration methods that allow for microscopic detection of motile parasites in fresh centrifugated samples. The testing will be performed on lymph node aspirate collected by needle biopsy and in the blood, using the Woo test (capillary tube centrifugation) or the mini-anion exchange centrifugation test (mAECT) (3) or, if concentration methods are not available, by examination of a thin blood smear or stained thick blood smear.

In the context of the study, the improved technique, called the “mini-anion exchange centrifugation test on buffy coats” (mAECT-BC) (4), will be used whenever possible in patients with positive serological tests and negative findings on the usual parasitological tests.

Because the serological tests currently available are not 100% reliable, an individual may have negative serological tests, but still show clinical signs suggestive of HAT. In this case, the individual will undergo the parasitological tests described above.

Current therapeutic options are not the same for early- and late-stage HAT and, as a result, before initiating treatment, it is necessary to determine the stage of the disease by analysing CSF collected on lumbar puncture. In usual practice, late-stage HAT is confirmed by the presence of parasites and/or of a CSF WBC above 5/ $\mu$ L. However, in clinical studies assessing treatments for late-stage HAT, the WHO recommends that a CSF WBC of 20/ $\mu$ L should be used as the threshold for determination of late-stage HAT (23). A CSF WBC of 20/ $\mu$ L will therefore be used as the threshold in this study.

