#### **4.2. Inclusion Criteria**

To be included in the study, the patient must fulfil all of the following criteria:

- Male or female
- 15 years of age or older
- Signed informed consent form (as well as assent from illiterate and under-age patients, and those unable to give consent)
- Karnofsky Performance Status above 50 (see Appendix 2; p83)
- Able to ingest oral tablets
- Having a permanent address or being traceable by other persons
- Able to comply with the schedule of follow-up visits and requirements of the study
- Agreement to be hospitalised in order to receive treatment.

For patients with late-stage HAT:

- Confirmation of g-HAT by detection of the parasite in the blood and/or the lymph and/or the CSF, at the investigational centre
- If trypanosomes are found in the blood or lymph, but not in the CSF, the CSF WBC, measured at the investigational centre, must be above 20/ $\mu$ L for the patient to be included in the cohort of patients with late-stage HAT

For patients with early- or intermediate-stage HAT:

- Confirmation of g-HAT by detection of the parasite in the blood and/or the lymph, at the investigational centre
- Absence of parasites in the CSF
- The CSF WBC, measured at the investigational centre, must be between 6 and 20/ $\mu$ L for the patient to be included in the cohort of patients with intermediate-stage HAT and equal to or below 5/ $\mu$ L for the patient to be included in the cohort of patients with early-stage HAT.

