**Table 1 : Classification of patients according to stage/severity at entry**

| Tryps in CSF               | WBC in CSF           |                                 |                      |
|----------------------------|----------------------|---------------------------------|----------------------|
|                            | ≤ 5/ $\mu$ l         | [6-20/ $\mu$ l]                 | > 20/ $\mu$ l        |
| Tryps in CSF (positive)    | Stage 2 (subgroup C) | Stage 2 (subgroup D)            | Stage 2 (subgroup E) |
| No tryps in CSF (negative) | Stage 1 (subgroup A) | Intermediate stage (subgroup B) | Stage 2 (subgroup F) |

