## 8.6. Efficacy analysis

### 8.6.1. Analysis of the primary efficacy endpoint

#### 8.6.1.1. Primary analysis

The primary analysis is the estimation of the success rate after 18 months of follow-up with acoziborole (cf. [Section 6.1](#)). The primary analysis will be performed on Stage 2 patients included in the mITT set.

An estimate of the success rate at 18 months will be provided. The 95% Jeffreys confidence interval of the estimate will be provided. The Jeffreys confidence interval has a coverage probability that does not exceed 95% by too much and is equal tailed, i.e. the probabilities of the interval lying above or below the upper and lower bounds are both close to 2.5%, which is important when the lower bound of the 95% confidence interval is more meaningful from a clinical standpoint than the upper bound.

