##### Stratification on confounding factors:

- Epicentre company used "Médecins Sans Frontières" (MSF) data to detect variables that are predictive of the response at 18 months (Priotto G et al. PLoS Negl Trop 2012).
- Five available variables significantly explained the outcome at 18 months:
  - Age

- Gender
- WBC count in CSF at baseline
- WBC at 6 months
- WBC at 12 months
- The first 3 factors: age according to 3 terciles (<T1, T1-T2, >T2), gender and WBC at baseline ( $\leq 100 / \mu\text{L}$ ,  $> 100 / \mu\text{L}$ ) could be used to create 12 strata. The stratification factor could then be included as a covariate in a CMH test or a log binomial model to get a within strata (blocks) comparison of treatments. This approach would be used as a sensitivity analysis.

The following advice was provided *“Data concerned late stage 2 patients treated with melarsoprol (n = 1469), eflornithine (n = 578) or a combination (n = 143). Moreover, death during treatment and follow-up were not included in the 2190 patients analyzed. At the time of submission of fexinidazole compound, a similar meta-analysis base on all patients treated with fexinidazole was performed using only baseline data as predictors of the outcome at month 18. A series of logistics models were fitted and the model reaching the lowest AIC (Akaike information criterion) was based on only one variable: the natural logarithm of the number of WBC in CSF at entry ( $p < 0.0001$ ). Other predictors (presence of trypanosome, age or other) had a larger AIC and consequently no interest or added value. Categorization of the number of WBC showed two pertinent thresholds:  $\text{WBC} \leq 100 / \mu\text{L}$  and  $\text{WBC} > 400 / \mu\text{L}$ ”*.

To meet SAWP (CHMP) request, it is planned:

- To keep the primary analysis as planned in the protocol.
- To use studies presented in Table 4 for the yardstick. One estimate would exclude NECT field (not randomized study and many dropouts) and another one would include NECT field.
- The natural logarithm of WBC in CSF at baseline could be used as covariate in a binary logistic model, i.e. outcome at 18 months (success vs. failure) according to treatment (NECT field versus Acoziborole) and natural logarithm of baseline WBC in CSF.

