### 9.2.15. Forest plot of success rate for the yardsticks

| Study                                     | Success rate (%) at M18 | Jeffrey 95% CL |
|---|-------------------------|----------------|
| 1. Mesu 2017 (Fex004) (success=124 / 130) | 95.4                    | 90.7-98.1      |
| 2. Priotto 2006 (success=16 / 17)         | 94.1                    | 75.6-99.4      |
| 3. Checchi 2007 (success=29 / 31)         | 93.5                    | 80.9-98.6      |
| 4. Priotto 2009 (success=135 / 143)       | 94.4                    | 89.7-97.3      |
| 5. Kansiime 2018 (success=50 / 55)        | 90.9                    | 81.2-96.4      |
| 6. Total (success=354 / 376)              | 94.1                    | 91.4-96.2      |
| 7. NECT field (success=582 / 613)         | 94.9                    | 93.0-96.5      |
| 8. DNDI-OXA-02-HAT (success=xxx / xxx)    | xx.x                    | xx.x-xx.x      |

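### The SAP is inconsistent about whether the acoziborole Stage 2 row and the NECT yardstick cover the same CSF white-cell range

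*SAP*

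**What the plan says.** **Cohort.** Protocol 4.2 makes the white-cell floor for the late-stage cohort conditional: "If trypanosomes are found in the blood or lymph, but not in the CSF, the CSF WBC" must exceed 20/µL. A patient with trypanosomes in the CSF has no floor. SAP Table 1 follows this. Its CSF-positive line reads "Stage 2 (subgroup C) | Stage 2 (subgroup D") for counts of 5 or fewer and of 6 to 20. SAP 8.6.1.1 then states: "The primary analysis will be performed on Stage 2 patients included in the mITT set". The primary population is therefore C+D+E+F, and template 9.2.15 plots it as one line, "8. DNDI-OXA-02-HAT (success=xxx / xxx"), under the NECT studies.

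**Yardstick.** SAP 8.6.1.4 describes the NECT data: "Data presented in Table 4 concerned patients in late stage 2 (WBC in CSF > 20) and are not matched on other inclusion criteria". SAP Table 2, in its FEX004 column, gives subgroups C and D the same late stage 2 label as E and F. FEX004 is the first row of Table 4. The WHO column of Table 2 marks C and D as categories not advised for second-stage trials.

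**Role of the count.** Protocol 1.3 reports that "in clinical studies assessing treatments for late-stage HAT, the WHO recommends that a CSF WBC of 20" cells/µL should mark late stage, and adopts 20 for this study. SAP 8.6.1.4 reports a fexinidazole analysis in which the best-fitting model used one baseline variable, "the natural logarithm of the number of WBC in CSF at entry" (p < 0.0001).

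**Use.** Protocol 9.6.2 and SAP 8.7 set no success rule. The observed rate and its lower bound are read against literature and historical data.

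**The concern.** With no control arm and no decision rule, the yardstick forest plot carries the efficacy conclusion. The regulatory advice quoted in SAP 8.6.1.4 asks the sponsor to consider matching or adjusting for population differences. A reader who takes that section at face value will think the rows already agree on CSF cell count and differ only elsewhere. The SAP's own cohort definition does not deliver that agreement, and its Table 2 contradicts the description for one of the largest yardstick rows.

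The planned adjusted analyses do not settle the matter. They depend on recovering other trials' databases. The logistic and CMH analyses name NECT field as comparator, a study left out of the pooled total. The lowest CMH stratum (100 cells or fewer) does not separate patients with 20 or fewer.

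**Working it through.** 1. **The plan's own figures reproduce.** The Jeffreys interval is taken from Beta(x + 0.5, n − x + 0.5). Table 4 rows sum to 124 + 16 + 29 + 135 + 50 = 354 successes in 130 + 17 + 31 + 143 + 55 = 376 patients. That is 94.1%, interval 91.4% to 96.2%, as stated. For planned precision, 138/155 = 89.0% gives 83.4% to 93.2%, as in protocol 9.1. No stated figure is disputed.

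2. **How much of the yardstick is in question.** FEX004 is 130/376 = 34.6%. For the other 376 − 130 = 246 patients, the documents give a CSF threshold only in the 8.6.1.4 sentence. Protocol section 4 calls the entry criteria similar to those of the 143-patient study, and the design the same as in WHO-TDR and FEX004. Those three studies hold 130 + 143 + 55 = 328 of the 376, but their CSF criteria are not given there.

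3. **Two readings.** If 8.6.1.4 is right, the acoziborole row contains C and D and the yardstick does not. If Table 2 is right, FEX004 could admit C and D, and 8.6.1.4 misdescribes that row. Both cannot hold for FEX004.

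4. **Possible size under the first reading.** Let f be the share of C+D in the Stage 2 cohort. Then shift = f × (success in C+D − success in E+F). The documents give none of these three inputs. Assume f from 5% to 30%, C+D success from 95% to 100%, and E+F success from 89% to 94%.
   - Smallest: 0.05 × (0.95 − 0.94) = 0.05 points.
   - Largest: 0.30 × (1.00 − 0.89) = 3.3 points.
   - If C+D succeed at the same rate as E+F, the shift is 0. If they do worse, it is negative.

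5. **What two rows would show.** Take 155 patients, E+F success near 89%, and C+D at 100% (the extreme case):

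| Assumed C+D share | E+F only (95% Jeffreys) | Width | Full row (95% Jeffreys) |
|---|---|---|---|
| 5% (8) | 131/147 = 89.1% (83.3 to 93.4) | 10.1 | 139/155 = 89.7% (84.2 to 93.7) |
| 10% (16) | 124/139 = 89.2% (83.3 to 93.6) | 10.3 | 140/155 = 90.3% (84.9 to 94.2) |
| 20% (31) | 110/124 = 88.7% (82.3 to 93.4) | 11.1 | 141/155 = 91.0% (85.7 to 94.7) |
| 30% (46) | 97/109 = 89.0% (82.1 to 93.8) | 11.7 | 143/155 = 92.3% (87.3 to 95.7) |

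   With E+F near 94% and a 20% share, E+F is 117/124 = 94.4% (89.2 to 97.4) and the full row is 148/155 = 95.5% (91.3 to 98.0). Part of each gap in the lower bound comes from the smaller n, not from case mix.

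**The case against.** A reader might infer more: that the acoziborole row contains easier-to-cure patients whom the yardstick excludes, so the comparison favours acoziborole. The documents do not support that.

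- **Exclusion is not established.** Table 2 points the other way for FEX004, and protocol section 4 suggests comparability for the main studies. Settling it needs the source trials.
- **Direction is not given.** SAP 8.6.1.4 does not say which way the count acts. Its model comes from fexinidazole-treated patients, and its useful thresholds are 100 and 400, not 20. The trend test in SAP 8.6.3 orders subgroups A, B, F, C, D, E, so C and D rank as more advanced than F. C and D do meet the white-cell part of success at entry, and the same model found no added value in trypanosome presence, so better prognosis is plausible. But success also requires parasite clearance, and these patients enter CSF-positive.
- **SAP 8.6.1.3 is not refuted.** Its statement that the possible bias disfavours acoziborole concerns how NECT losses and missing assessments were classified. It does not address case mix.
- **Protocol 1.3 and 4.2 need not conflict.** Adopting 20 can be read as replacing 5 in the white-cell part of the usual definition, leaving CSF parasites sufficient on their own.

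It is also fair to say that much is already planned. SAP 8.6.3 gives the E+F rate descriptively, results are shown by subgroup, and subgroup shares are reported. What stands is that the E+F rate stays in an exploratory table away from the yardstick plot, and that the two descriptions of the yardstick disagree.

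**Conclusion.** The point holds as an inconsistency with a practical consequence, not as a demonstrated bias. The acoziborole row covers all CSF counts among CSF-positive patients. The SAP describes the yardstick as above 20 cells and contradicts this for FEX004, about 35% of the pooled patients. The sponsor has something to correct on either reading.

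The direction and size of any effect on the comparison cannot be determined, because the C+D share and the direction of the white-cell effect are not given. The range of about 0 to 3 points rests wholly on the assumed values and on C+D doing at least as well as E+F. Three points would be noticeable beside the planned interval width of 9.8 points at 89%; the low end would not. The remedy is cheap enough to be worth making without knowing which case applies.

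**What to change.** Keep the primary analysis and the full Stage 2 row unchanged.

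1. Add to Table 4 the CSF entry criterion of each NECT study, and correct either the 8.6.1.4 sentence or the FEX004 column of Table 2 so that they agree. Do this first, because it decides how the rows may be read.
2. In output 14.2.1.3 (template 9.2.15), add a second acoziborole row limited to subgroups E+F (CSF WBC above 20) with its Jeffreys interval, using the rate already planned in SAP 8.6.3.
3. State that the E+F row is read only against yardstick rows confirmed as above 20 cells, and the full row against studies that also admitted CSF-positive patients at any count. Without this rule, E+F set against a study that admitted C and D would create the opposite mismatch.

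Protocol 9.4 also promises a baseline table for each NECT study, which the study-patient outputs in SAP 9.1.1 do not list. Supplying it would help with step 1.

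The cost is one plot row, one table column and a few sentences. The E+F row has fewer patients: at about 89% success its interval is roughly 10.1 to 11.7 points wide for assumed C+D shares of 5% to 30%, against 9.8 for all 155.

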##### Stratification on confounding factors:

- Epicentre company used "Médecins Sans Frontières" (MSF) data to detect variables that are predictive of the response at 18 months (Priotto G et al. PLoS Negl Trop 2012).
- Five available variables significantly explained the outcome at 18 months:
  - Age

- Gender
- WBC count in CSF at baseline
- WBC at 6 months
- WBC at 12 months
- The first 3 factors: age according to 3 terciles (<T1, T1-T2, >T2), gender and WBC at baseline ( $\leq 100 / \mu\text{L}$ ,  $> 100 / \mu\text{L}$ ) could be used to create 12 strata. The stratification factor could then be included as a covariate in a CMH test or a log binomial model to get a within strata (blocks) comparison of treatments. This approach would be used as a sensitivity analysis.

The following advice was provided *“Data concerned late stage 2 patients treated with melarsoprol (n = 1469), eflornithine (n = 578) or a combination (n = 143). Moreover, death during treatment and follow-up were not included in the 2190 patients analyzed. At the time of submission of fexinidazole compound, a similar meta-analysis base on all patients treated with fexinidazole was performed using only baseline data as predictors of the outcome at month 18. A series of logistics models were fitted and the model reaching the lowest AIC (Akaike information criterion) was based on only one variable: the natural logarithm of the number of WBC in CSF at entry ( $p < 0.0001$ ). Other predictors (presence of trypanosome, age or other) had a larger AIC and consequently no interest or added value. Categorization of the number of WBC showed two pertinent thresholds:  $\text{WBC} \leq 100 / \mu\text{L}$  and  $\text{WBC} > 400 / \mu\text{L}$ ”*.

To meet SAWP (CHMP) request, it is planned:

- To keep the primary analysis as planned in the protocol.
- To use studies presented in Table 4 for the yardstick. One estimate would exclude NECT field (not randomized study and many dropouts) and another one would include NECT field.
- The natural logarithm of WBC in CSF at baseline could be used as covariate in a binary logistic model, i.e. outcome at 18 months (success vs. failure) according to treatment (NECT field versus Acoziborole) and natural logarithm of baseline WBC in CSF.
- The analysis set could be split in 3 strata according to the following threshold: baseline WBC in CSF  $\leq 100 / \mu\text{L}$  and  $> 400 / \mu\text{L}$ . A CMH test could then be performed for the comparison, i.e. outcome at 18 months (success vs. failure) according to treatment (NECT field versus Acoziborole), adjusted for the 3 strata.
- The natural logarithm of WBC in CSF at baseline and other available baseline data (presence of trypanosomes in CSF, age, gender, and possibly other available covariates) could be used as covariates in a binary logistic model to obtain a propensity score. The analysis of the outcome at 18 months could then be adjusted using propensity score.
- The last 3 analyses would be considered as sensitivity analyses.

### 8.6.2. Analysis of the secondary efficacy endpoints

#### Efficacy analysis in stage 1 and intermediate-stage patients

The efficacy analysis for stage 1 and intermediate-stage patients is a secondary analysis. It concerns the success rate at 6 months, 12 months and at 18 months in stage 1 and intermediate-stage patients. The same analyses as described for the primary endpoint will be provided (cf. [Section 8.6.1](#) “Primary analysis” and “Sensitivity analyses”).

Note: the yardstick for this cohort will be pentamidine and possibly newly registered treatment.

#### Secondary efficacy analysis in stage 2 patients

The success rate at 6 months and 12 months in stage 2 patients will be analyzed as described for the primary endpoint (cf. [Section 8.6.1](#) “Primary analysis” and “Sensitivity analyses”).

**Analysis of the overall success rate at 18 months**

The overall success rate at 18 months (i.e. whatever the stage of HAT) will be calculated, along with the 95% Jeffreys confidence interval.

Three estimates will be provided:

- (1) On all patients included in the mITT set, excluding patients with stage 1 and intermediate stage HAT screened before the 20JUN2017, i.e. before recruitment of stage 1 and intermediate stage HAT patients has been authorized by the 1st DSMB meeting; corresponding to date of email from DNDI sent to the sites to allow inclusion of patients with stage 1 and intermediate stage HAT). In that case cohorts are self-weighted.
- (2) On all patients included in the mITT set, weighted by the duration of inclusion of each cohort. If the recruitment rate is far to be constant over time, i.e. if the cumulated number of recruited patients in each cohort taken separately is far to be linear, a piecewise estimate of the weight will be done.
- (3) On all patients included in the mITT set (\*)

(\*) Note: for the third estimate, the success rate after 18 months will be compared between “stage 1 + intermediate-stage patients” and “stage 2 patients” using a Fisher test. If there is no statistically significant difference, the estimate of the overall success rate will be provided. Otherwise, the third estimate will not be provided.

In case of a clinically significant difference between the 3 estimates, the second estimate will be used as it is the only one which takes into account all patients and is weighted by the estimated proportion of patients belonging to each sub-population.

Note: the yardstick for this endpoint will be fexinidazole and possibly newly registered treatment.

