### **9.1. Sample Size Determination**

The sample size is based on the largest number of patients who can be enrolled within a reasonable timeframe. It is expected that 155 late-stage patients should be enrolled within approximately 2 years. A provision of 5% (7 patients) is planned in order to allow for replacement of patients lost to follow-up who fled the region due to armed conflict or natural disaster. Approximately 50 early- and intermediate-stage patients could be enrolled within this timeframe. As a reminder, enrolment of early- and intermediate-stage patients will begin approximately 6 months after the start of enrolment of late-stage patients and will end at the same time.

If the observed success rate is around 89% (the same as the expected rate for fexinidazole and the observed rate with eflornithine) then the width of the 95% Jeffreys confidence interval will be 9.8% (83.4%–93.2%) for an 89% success rate. The width decreases with an increase in the success rate to reach 7.4% (89.7%–97.1%) for a 94% success rate. In contrast, the precision is not highly sensitive to the sample size. With 200 patients, the width of the confidence interval is 8.7% (84.1%–92.8%) for an 89% success rate. Indeed, the sample size must increase by 50%, i.e. 300 patients instead of 200, to reduce the width of the lower arm of the 95% confidence interval by one percentage point.

In early- and intermediate-stage patients, the expected success rate is around 91%, i.e. the same as for pentamidine. The width of the confidence interval with 50 patients will be of the order of 17%.

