### 4.1. Study Design

Cf. Section 3 of the Protocol:

“This is a multicentre, prospective, open-label, non-randomised, phase II/III study to assess the efficacy and safety of acoziborole in two cohorts of patients with g-HAT. The first cohort will be composed of patients with late-stage HAT, and the second cohort will be composed of patients with early- or intermediate-stage HAT”.

“Early- and intermediate-stage patients will be enrolled in the same centres as late-stage patients, however enrolment of early- and intermediate-stage patients will begin approximately 6 months later, once the Data and Safety Monitoring Board (DSMB) has examined the PK and safety data at 3 months for the first 20 patients with late-stage HAT and once it has been informed of the results of the first futility analysis”.

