### 7.2. Type I error

For all analyses, the type I error ( $\alpha$ ) is set to 0.05, two sided.

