**14.2.2.2.12 Overall success rate at 18 months (whatever the stage of HAT)**

14.2.2.2.12.1: Overall success rate at 18 months (mITT, excluding patients with stage 1 and intermediate stage HAT screened before the 20JUN2017)

14.2.2.2.12.2: Overall success rate at 18 months (mITT, weighted by the duration of inclusion of each cohort)

14.2.2.2.12.3: Comparison in success rate at 18-months between stage 1 and intermediate-stage patients versus stage-2 patients (mITT)

14.2.2.2.12.4: Overall success rate at 18 months (mITT)

*Note: as written in section 8.6.2, this table will not be provided if the previous comparison is statistically significant.*

14.2.2.2.12.5: Overall success rate at 18 months giving equal weight to each centre (mITT)

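### Overall success rate, estimate (1): the date filter removes the wrong cohort, so the estimate is not self-weighted and reproduces the unweighted estimate (3)

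*SAP*

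**What the plan says.** SAP 8.6.2 (overall success rate at 18 months) defines three estimates:

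- **Estimate (1):** the mITT set, "excluding patients with stage 1 and intermediate stage HAT screened before the 20JUN2017". The SAP explains that this is the date on which sites were allowed to include such patients, and adds: "In that case cohorts are self-weighted".
- **Estimate (2):** all mITT patients, weighted by how long each cohort was open to inclusion.
- **Estimate (3):** all mITT patients without weights. It is reported only if Fisher's test finds no significant difference between the cohorts. Under SAP 7.2 the significance level "is set to 0.05, two sided".

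If the three differ to a clinically significant degree, estimate (2) is used. The output list repeats the filter of estimate (1) in the title of output 14.2.2.2.12.1: "mITT, excluding patients with stage 1 and intermediate stage HAT screened before the 20JUN2017".

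On timing, SAP 4.1 says that "enrolment of early- and intermediate-stage patients will begin approximately 6 months later", after the DSMB has reviewed the first 20 late-stage patients. Protocol 9.1 adds that this enrolment "will begin approximately 6 months after the start of enrolment of late-stage patients and will end at the same time". SAP Section 5 admits to the mITT set only patients who took at least one tablet.

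**The concern.** A pooled sample reflects the natural mix of stages only if both cohorts are counted over the same open period. The imbalance here comes from the months when only stage 2 patients were being enrolled. Removing it means dropping the stage 2 patients screened before 20JUN2017. The SAP drops the other cohort from that period, and that cohort was not yet open.

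Three things follow:

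- Estimate (1) lacks the property the SAP claims for it.
- The comparison of three estimates, which decides whether estimate (2) takes over, is partly a comparison of one number with itself.
- The unweighted pooled rate, which the Fisher rule is meant to hold back when the cohorts differ, would still be reported as estimate (1), described as self-weighted.

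**Working it through.** **Inputs**

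- Stage 2: 155 patients (Protocol 9.1: "It is expected that 155 late-stage patients should be enrolled within approximately 2 years").
- Cohort 2 (stage 1 plus intermediate): 50 patients (Protocol 9.1: "Approximately 50 early- and intermediate-stage patients could be enrolled within this timeframe").
- Lead of stage 2: 6 months, with a common end of enrolment (Protocol 9.1).
- Enrolment period T: 28 months (Protocol Section 7) or 24 months (the 2 years of Protocol 9.1). Both are used.
- Planning success rates: 89% for stage 2 and 91% for cohort 2 (Protocol 9.1). Protocol 9.1 also considers 94% for stage 2. Cohort 2 rates of 98% and 100% are my assumptions, used to show the range.
- Constant accrual within each cohort is assumed.

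**The plan's own figures.** The 95% Jeffreys interval takes the 2.5% and 97.5% quantiles of Beta(x + 0.5, n − x + 0.5). For 138/155 it is 83.4–93.2% (width 9.8), for 146/155 it is 89.7–97.1% (width 7.4), and for 178/200 it is 84.1–92.8% (width 8.7). All three match Protocol 9.1. The documents give no figure for the overall rate itself.

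**Stage 2 patients enrolled before cohort 2 opened:** 155 × 6/T = 33.2 (T = 28) or 38.8 (T = 24).

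**Weights**

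| Estimate | Stage 2 share | Cohort 2 share |
|---|---|---|
| (1) as the SAP words it | 155/205 = 75.6% | 50/205 = 24.4% |
| (3) unweighted | 75.6% | 24.4% |
| (1) with early stage 2 removed, T = 28 | 121.8/171.8 = 70.9% | 29.1% |
| (1) with early stage 2 removed, T = 24 | 116.25/166.25 = 69.9% | 30.1% |

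The duration weight for cohort 2 in estimate (2) is [50/(T − 6)] / [50/(T − 6) + 155/T]. This gives 29.1% (T = 28) and 30.1% (T = 24), the same as estimate (1) with the filter moved to stage 2. So moving the filter produces self-weighting, and the SAP's filter produces estimate (3).

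**Effect on the pooled rate.** The shift equals the change in cohort 2 share times (cohort 2 rate − stage 2 rate).

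| Stage 2 / cohort 2 rate | (1) as worded = (3) | (1) corrected, T = 28 to 24 | Shift (points) |
|---|---|---|---|
| 89% / 91% | 89.49% | 89.58–89.60% | 0.09–0.11 |
| 94% / 98% | 94.98% | 95.16–95.20% | 0.19–0.23 |
| 89% / 98% | 91.2% | 91.6–91.7% | 0.4–0.5 |
| 89% / 100% | 91.68% | 92.20–92.31% | 0.52–0.63 |

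**The Fisher rule.** With 138/155 and 50/50 successes, Fisher's p = 0.015, so estimate (3) = 188/205 = 91.7% (Jeffreys 87.3–94.9%) is withheld. Estimate (1) would show the same rate and interval. By exact enumeration over two binomials (155 and 50), the probability that (3) is withheld is 4.5% at 89%/91%, 8.3% at 94%/98% and 92.9% at 89%/100%.

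**The case against.** The best case against this point is that little depends on it. The all-stage rate is a secondary endpoint introduced by the SAP, the primary stage 2 analysis is untouched, and the trial has no formal success rule. At the planning rates the shift is about 0.1 points, against a pooled interval about 7.6 points wide in the 188/205 example. Estimate (2) is correctly weighted and takes over if the estimates differ clinically. All of this is true and limits the severity. But gaps this small are unlikely to trigger the switch to (2), so estimate (1) would stand with a property it does not have.

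Four narrower objections:

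- **Estimate (1) is reported whatever the Fisher result, even after correction.** True: a pooled rate will appear either way. The fault is that it would be the unweighted figure the rule withholds, under another description.
- **Under constant accrual, corrected (1) has the same weights as (2).** True, so the two should agree closely. They reach those weights by different routes, one by restricting patients and the other by weighting all of them, and can differ if accrual or success rates vary over time.
- **The count of 33–39 patients is a planning figure.** True. The documents give no first-patient date and say only about 6 months. The one documented floor is the 20 stage 2 patients needed for the first DSMB review. With 20, the stage 2 share is 135/185 = 73.0% and the shift at 89%/91% is about 0.05 points. The count could also exceed 39.
- **The identity of (1) and (3) is inferred.** Screening may precede dosing by up to 15 days (Protocol 4.1), so a few cohort 2 patients could have been screened before the date and treated after it. Removing one to three of them lowers the cohort 2 share to 24.0–23.3%, further from self-weighting.

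**Conclusion.** The point holds. The filter in estimate (1) acts on the cohort that had not yet opened, removes essentially nobody from the mITT set, and leaves in the early stage 2 patients who cause the imbalance. The claim of self-weighting is wrong, and estimate (1) is in practice estimate (3) without its reporting condition.

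The stage 2 weight is 75.6% where the common enrolment period would give 69.9–70.9%. The pooled rate moves by about 0.1 points at the planning rates and by 0.5–0.6 points at 89%/100%. These sizes assume 155 and 50 patients, a 6-month lead and constant accrual over 24 to 28 months. The logical error does not depend on them, provided stage 2 enrolment was open before 20JUN2017, as the plan describes. This should be corrected before the analysis, but it does not threaten the primary result.

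**What to change.** Reword estimate (1) in SAP 8.6.2 and the title of output 14.2.2.2.12.1 along these lines: *mITT patients of either cohort screened on or after 20JUN2017; stage 2 patients screened before that date are excluded.* The statement on self-weighting can then stay.

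The cost is one sentence, one output title and one program filter; no new data are needed. Estimate (1) would use about 33–39 fewer patients (166–172 in place of 205). At a similar success rate its interval widens by a factor of roughly √(205/171.8) = 1.09 to √(205/166.25) = 1.11. Estimate (2) still uses every patient.
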